## **2.5 CB-103 – PAN-NOTCH TARGETING DRUG CANDIDATE**

CB-103 is an orally bioavailable synthetic small molecule (Molecular weight: 278.78 g/mol) and a first-in-class pan-NOTCH inhibitor. It targets the NOTCH signalling pathway in its most downstream part by binding to the NOTCH-specific transcription complex located in the cell nucleus. CB-103 is an oral drug administered as a capsule. In animals, the compound is rapidly absorbed after administration, distributes rapidly into tissue and diffuses into the nucleus of malignant cells, binds to the transcription complex and inhibits translation and protein expression of NOTCH-related target genes which are responsible for the various functions NOTCH can trigger and modulate in many fundamental processes and in a wide range of tissues.

### **2.5.1 Mechanism of Action**

After entering the tumour cells, CB-103 translocates to the cell nucleus and binds to the NOTCH-specific transcription complex hindering subsequent binding of the NICD and therefore blocking the transcription and translation of the NOTCH target genes. The molecular target and binding site of CB-103 at the NOTCH-specific transcription complex has been identified. Two pharmacodynamics studies were conducted to confirm the mechanism of action and characterise the cellular target of CB-103 at the transcription complex. Further details on these studies can be found in the Investigator's Brochure.

### **2.5.2 Non-Clinical Pharmacology**

A summary of the *in vitro* and *in vivo* pharmacology studies is given in the Investigator's Brochure.

#### **2.5.2.1 Safety Pharmacology**

Single oral doses of CB-103 at 10, 30 and 80 mg/kg had no effect on respiratory function in the rat. In addition, CB-103 at 10 mg/kg was devoid of effects on the CNS in the rat.

Single oral doses of CB-103 up to and including 200 mg/kg had no effect on blood pressure and heart rate in the conscious telemetered rat. Likewise, the compound had no effect on blood pressure, heart rate or the PR and RR intervals of the electrocardiogram (ECG) in the conscious dog when administered as a single dose up to 26.3 mg/kg or two doses of 10 mg/kg given 12 hours apart.

CB-103 at 0.8 mg/kg had no effect on the QRS complex (QRS) QT interval corrected for heart rate or (QTc) intervals of the ECG.

The higher doses of CB-103 caused an increase in the QTc in dogs. These increases in QTc were transient with a single time point at 0.5 hour post-dose being statistically significant following treatment with 7.8 mg/kg and values up to 6.0 hours post-dose being statistically significant after the top dose (26.3 mg/kg). Similar effects on the QTc interval were observed when CB-103 was given as two 10 mg/kg doses 12 hours apart. The plasma concentrations associated with these effects are estimated to be  $\gg 3000$  ng/mL total CB-103 (free concentration  $\gg 90$  ng/mL) and the most likely mechanism for the effect of CB-103 on the QTc interval in the dog is inhibition of the hERG-mediated potassium current ( $IC_{50} = 38.5 \mu M = 9333$  ng/mL) and the inhibition of L-type calcium channel (hCav1.2) at lower concentrations ( $IC_{50} = 26.88 \mu M = 6516$  ng/mL). Compounds with this profile (greater calcium antagonist potency than hERG) have been shown to have a lower pro-arrhythmic potential than 'pure' hERG blockers and therefore CB-103 may have a low risk for Torsades de Pointes arrhythmia in man (Kramer et al., 2013b).

CB-103 at a dose of 0.8 mg/kg had no effect on the QRS interval in the dog. However, the higher doses of 7.8 and 26.3 mg/kg caused a dose-related increase in the QRS interval, with the duration of action being longer at the top dose (~6 hours) than that observed at the mid-dose (~1 hour). These effects were also associated with some morphological changes in the ECG waveform in 2 of 4 dogs after 7.8 mg/kg and in all 4 dogs after 26.3 mg/kg. Prolongation of the QRS interval is indicative of the slowing of conduction through the heart and the most likely mechanism for this effect is inhibition of cardiac sodium channels ( $Na_v1.5$  ( $IC_{50} = 58.9 \mu M$  to  $60.66 \mu M$ )). Cardiac sodium channel blockers can also reduce the force of contraction of the heart and this may explain the small increase in the QA interval observed in dogs treated with CB-103 at doses of 7.8 and 26.3 mg/kg.

Thus, these data suggest that CB-103 has some potential to affect cardiac repolarisation and cardiac conduction and careful monitoring of the ECG will be warranted in human clinical trials.

Gastrointestinal (GI) safety studies revealed for CB-103-treated mice completely normal intestinal tissues and no indication of goblet cell accumulation. At an increased dosing frequency (3 x daily), CB-103 exhibited a mild intestinal toxicity apparent by an increase in goblet cell population in the intestine. In the spleen, CB-103 mediated inhibition of NOTCH2 signalling led to more than 90% reduction in the MZB confirming its *in vivo* activity. Overall in all animal studies performed in different species (mice, rats and dogs) and with different doses and schedules of CB-103, there were no signs of diarrhoea reported suggesting that the typical gastro-intestinal toxicities seen caused by the goblet

cell metaplasia reported for the other classes of NOTCH inhibitors, may not be the key toxicity driver and limiting-factor with regards to exposure for CB-103.

### **2.5.3 Pharmacokinetics**

#### **2.5.3.1 Animal Pharmacokinetics and Drug Metabolism**

The absorption, distribution, metabolism, and excretion (ADME) profile of CB-103 has been investigated in *in vitro* and *in vivo* studies and the repeat dose PK in rats and dogs was assessed as part of the toxicokinetic program. The study results are summarised in this section and more detailed information can be found in the Investigator's Brochure.

CB-103 shows excellent drug-like properties based on the pre-clinical *in vitro* and *in vivo* ADME profile. The compound is highly permeable and well absorbed after oral administration with a time at which the maximum serum concentration ( $C_{max}$ ) is observed ( $t_{max}$ ) of about 1 hour. CB-103 is not a substrate for P-Glycoprotein (Pgp). Bioavailability after various formulations given to mice and dogs is high or complete. Rats show a lower bioavailability most likely due to a combination of high first pass metabolism and potentially incomplete absorption.

Despite its high binding to plasma proteins from various animal species and humans ( $\geq 97\%$ ) CB-103 distributes widely into the body and was detectable in brain, kidney, liver, spleen and skin tissues from rats. The elimination of CB-103 in animals is relatively fast (elimination half-life [ $t_{1/2}$ ]: 2 hours in mice, 3 hours in rats and 7-10 hours in dogs), and no signs of significant accumulation have been observed with daily dosing. The expected  $t_{1/2}$  in humans is around 16 hours (see Section 2.5.3.2) Overall, the PK parameters after first and repeated administration were comparable, except for a decrease in exposure over time during the 28-day Good Laboratory Praxis (GLP) toxicity study in dogs at all doses and in both genders. No explanation for this observation has been found, but the exposure coverage at the end of this study was still sufficient to allow a valid assessment of CB-103 toxicity in dogs for the calculation of safety margins.

In general, the PK of CB-103 is dose proportional, with a tendency to higher than dose proportional exposure in dogs in the range of 1 to 10 mg/kg/day. At 50 mg/kg given to dogs absorption of CB-103 is delayed and the  $C_{max}$  is lower than expected. In rats an absorption plateau is reached with 200 mg/kg.

All human metabolites formed in hepatocytes are covered by the toxicology species (rats and dogs), but some species differences have been observed with respect to CB-103 metabolism. The predominant metabolic conversion of CB-103 in rodents, monkey and humans seems to be N-acetylation. Oxidative metabolism occurs as well, but seems to play a minor role in humans. Dogs are deficient of the enzymes catalysing N-acetylation (N-acetyltransferase [NAT] isoforms 1 and 2) and have a lower intrinsic clearance (CL) of CB-103. The predominant metabolic route of clearance in the dog is oxidative metabolism combined with glucuronidation.

The involvement of NAT1/NAT2 in the metabolism of CB-103 in humans might be of relevance since NAT polymorphism results in high- and low metabolizing individuals. Metabolic stability of CB-103 in human hepatocytes from individuals genotyped as slow, intermediate and fast NAT metabolizers showed a relationship of metabolic *in vitro* turnover and genotype. Genotyping patients for polymorphisms of metabolising enzymes to understand its impact on the clinical PK of CB-103 is foreseen in the clinical protocol (refer to the Schedule of Assessments). Preliminary results of these pharmacogenetic investigations exploring the potential influence of NAT genotypes on the PK of CB-103 have not revealed any correlation or effect on the pharmacokinetics of CB-103.

### 2.5.3.2 Prediction of Human PK from Non-Clinical Studies (Allometric Scaling)

Allometric scaling for CB-103 using mouse, rat and dog intravenous (i.v.) PK data was performed to predict the human PK parameters CL, volume of distribution at steady state ( $V_{ss}$ ) and  $t_{1/2}$ .

Table 2 summarises the prediction along with the input values for the scaling. No correction for plasma protein binding was performed as the differences across species is minimal (binding approx. 98% in all species).

**Table 2** Pharmacokinetic parameters observed in mouse, rat and dog and predicted for humans using allometric scaling

Species	Mouse	Rat	Rat	Dog	Human
Data Source	CB-103-ADME010	CB-103-ADME011	CB-103-T002	CB-103-T001	PREDICTED
Body weight	0.025 kg	0.3 kg	0.38 kg	12 kg	70 kg
CL (mL/h/kg)	3627.5	2481.3	3940	456	
CL (mL/h)	90.7	744.39	1497.2	5472	23520
Vss (mL/kg)	1664.8	1125.3	897	5670	
Vss (L)	0.042	0.338	0.341	68.0	380
T1/2 (h)	0.49	0.73	0.157	10.2	16.2
Bioavailability (F)	100%	16.3%	15.4%	81%	
Plasma Protein Binding (%)	98.3	98.2		98.7	97.0

Data in bold are measured, data in italics are calculated. Parameters for humans are predicted.

For the human predicted values of CL 23520 mL/h (or 23.52 L/h) and of  $V_{ss}$  380 L, the estimated half-life ( $V_{ss}/CL$ ) is around 16 hours. It is therefore expected that CB-103 needs about 3 to 4 days to reach steady state concentrations. With daily administration, the predicted accumulation ratio (AR) would be 1.5. The first dose level administered in this clinical protocol is 15 mg (fixed dose) and the expected AUC at this dose is 639  $\mu\text{g}\cdot\text{h}/\text{mL}$

assuming complete bioavailability of the compound after oral administration. If the bioavailability of CB-103 in humans is less than 100% the exposure will be respectively lower.

#### **2.5.4 Animal Toxicology and Toxicokinetics**

The pre-clinical safety and toxicology package presented for CB-103 determined the tolerability of the compound in rodent and non-rodent species over a wide range of doses and exposure levels.

The assessment of the safety of CB-103 in rats and dogs demonstrates a safety profile commensurate with administration to cancer patients. A finding common to both rat and dog toxicology studies with CB-103 was reduced thymus weight with accompanying histological changes. Effects in the thymus, as described in rats and dogs dosed with CB-103, are commonly associated with stress induced by many different stressors, including high systemic exposure to xenobiotics (Everds et al., 2013), therefore these are not a safety risk for humans.

The liver was a target organ in both rats and dogs. In rats, hypertrophy and resultant increased liver weight are indicative of an adaptive response due to the presence of large amounts of a xenobiotic present in the liver. Likewise, the hepatomegaly and histological changes that occurred in the MTD study are considered due to the presence / accumulation of large amounts of compound. Of note, no changes occurred in livers of dogs from the 28-day GLP study, therefore the changes in the livers of rats and dogs given high doses of CB-103 are not a toxicological risk to cancer patients.

In both rats and dogs, dilation of the pupils occurred. In rats this effect was evident at doses of 10 and 30 mg/kg/day (GLP 28-day study). In dogs this was evident at all doses in the GLP 28-day study (1, 3, 10 mg/kg/day) and at 25 mg/kg/day in the non-GLP MTD/fixed-dose study. In rats, retinal atrophy was present in females at the end of the 28-day GLP study and was still present at the end of the recovery period. Retinal atrophy was also present in males at the end of the recovery period whereas it was not present at the end of the dosing period. The exact mechanism of retinal atrophy caused by CB-103 remains unclear, however it is consistent with observations in albino rats exposed to excess light (De Vera Mudry et al, 2013), therefore the retinal degeneration is considered secondary to dilation of the pupils. Importantly, retinal atrophy was not present in dogs and is therefore not expected in humans. No specific eye exams are foreseen in the clinical protocol, but pupil size in patients will be monitored as part of the regular physical examination occurring at every study visit.

Severe toxicity and unscheduled death were only observed at very high doses given repeatedly to rats and dogs leading to exposure levels above 4000 ng/mL ( $C_{max}$ ) and 30,000 ng\*h/mL ( $AUC_{0-24}$ ). The 28-day GLP toxicity studies in rats and dogs determined 10 mg/kg/day and 2.6 mg/kg/day as the no observed adverse effect level (NOAEL), respectively with minimal signs of toxicity and exposure levels of approx. 300-500 ng/mL ( $C_{max}$ ) and approx. 1300-3400 ng\*h/mL ( $AUC_{0-24}$ ). The findings at the next higher dose

levels in both species were still mild and reversible. The observations in rats at 30 mg/kg/day included transient clinical signs (ploughing, salivation, decreased activity and pale/dark eyes), decreased body weight gain, changes in haematology, clinical chemistry parameters and increased liver and spleen weights correlating with erythropoiesis in the spleen and hypertrophy on the liver. The observations at 8.6 mg/kg/day in dogs included dilated pupils, pale skin and gums, rimmed eyelids and lacrimation, decreased activity, apparent pain, changes in thymus and spleen and an increased reticulocyte count. Therefore, 30 mg/kg/day in rats and 8.6 mg/kg/day in dogs are considered the highest non-severely toxic doses (HSNTD) with exposure levels of approx. 1200-3100 ng/mL ( $C_{max}$ ) and 6000-9000 h.ng/mL ( $AUC_{0-24}$ ). The starting dose in humans (15 mg) targets an  $AUC_{0-24}$  of 600 h.ng/mL after repeated administration (Section 2.5.3.2), which equals 1/10th of the HSNTD in the most sensitive species (rat  $AUC_{0-24}$  on Day 28 at 30 mg/kg/day 5980 h\*ng/mL in male rats).

CB-103 is not mutagenic in the *S. typhimurium* tester strains (TA1537 or TA98) or *E. coli* reverse mutation assay strain WP2uvrA. The positive results from the S9-mix showing mutagenic response with the tester strains TA1535 and TA100 of *S. typhimurium* in the presence of S9-mix suggest that metabolites of CB-103 generated in the presence of S9-mix might be mutagenic. However, no additional studies were performed as these were not required according to the “ICH S9 Nonclinical evaluation for anticancer pharmaceuticals Guideline” to support clinical trials for therapeutics intended to treat patients with advanced cancer.

## 2.5.5 Biomarker Development

Biomarkers are objectively measured and evaluated indicators of normal biological processes, pathogenic processes, or pharmacologic responses to a therapeutic intervention. Multiple potential biomarkers relevant to the NOTCH signalling pathway and mechanism of action of CB-103 have been incorporated into this study to explore the relationship between the expression or presence of appropriate markers and clinical outcome. In addition, the PD effects of CB-103, including their usefulness in determining the recommended phase 2 dose based on considerations for optimal biological dosing of CB-103 will be explored. The success of the overall biomarker strategy will be dependent on obtaining sufficient tumour material at pre- and post-treatment with CB-103 at a selected time point after the initiation of CB-103 dosing.

### 2.5.5.1 Patient Profiling Biomarkers

Various biomarker approaches to detect genetic aberrations of NOTCH signalling and to characterise the functional level of NOTCH activation have shown to be of value with regards to the prognostic value that these NOTCH aberrations have in terms of poorer survival seen in patients of different tumour indications, as well as to be used to select the right patient population for treatment with a NOTCH inhibitor (Takebe et al., 2015). As there are different genetic alterations of the NOTCH pathway, known to cause NOTCH over- and constitutive activation and that their functional role may be different in different

cancer indications, there will be a need to develop and apply several methods to detect and characterise these in tumour samples.

NOTCH1-mutant ACC tumors have demonstrated significantly higher levels of Notch1 pathway activation than wild-type tumors on the basis of Notch1 intracellular domain staining. NOTCH1 mutations define a distinct disease phenotype characterized by solid histology, liver and bone metastasis, poor prognosis, and potential responsiveness to Notch1 inhibitors (Ferrarotto et al 2016).

The use of NOTCH-specific biomarkers and different methods used for their detection for patient selection will be explored in Part A (escalation) in a retrospective fashion, whereas it will be prospectively applied for patient selection in Part B (expansion) of the study. Characterisation of functional NOTCH activation in tumour samples will be based on detection of the different genetic aberrations of the NOTCH signalling pathway found in various cancer indications and/or the characterisation of the activation level of NOTCH signalling at the protein and/or RNA level.

Genetic mutations of the NOTCH pathway known to cause over-activation of NOTCH signalling (such as single nucleotides variations, InDels, structural variations (rearrangements), copy number variations) will be assessed by next-generation sequencing (NGS). NICD1 IHC and/or gene expression analysis can also be used to assess NOTCH pathway activation.

Details on the collection, handling and processing of the required specimens for the diagnostic (patient selection) and exploratory biomarker studies will be provided in a separate Laboratory Manual.

### **2.5.5.2 Pharmacodynamic Markers of NOTCH Inhibition**

The available published data show that NOTCH inhibitors produce demonstrable PD effects, such as the reduction of NOTCH pathway components (e.g. NOTCH NICD) and the down-regulation of various NOTCH target genes in both tumours and surrogate tissues.

For GSI treatment reports have shown that measurement of NOTCH1 NICD by immunohistochemical (IHC) staining (Kluk et al., 2013) and HES-1 and HES-4 as NOTCH target genes represent the most promising predictive biomarkers of response to NOTCH-targeted therapies in TNBC and ACC (Stoeck et al., 2014).

In this clinical study, NOTCH inhibition will be assessed in whole blood and plasma samples, in hair follicles and available tumour specimens (pre- and post-treatment) by evaluating several PD markers of target modulation and mode of action such as the reduction of certain NOTCH-related components of the pathway, as well as the modulation of key NOTCH-specific and -related genes.

Technologies as NGS and nCounter Nanostring gene expression analysis will be used to detect the different genetic lesions of the NOTCH pathway, and the expression of the functional target genes at the molecular level. IHC or Western Blot may be used to assess expression levels of NOTCH pathway related proteins. The oncogenic function of NOTCH

signalling is well understood and can be detected in various solid tumour indications and frequently in numerous haematological malignancies.

Details on collection, handling and processing of the required specimens for the PD biomarker analysis will be provided in a separate Laboratory Manual.

### **2.5.5.3 Pharmacodynamic Markers of Cellular Effects**

The response biomarkers for NOTCH inhibitors primarily include tumour or cellular effect markers that indicate changes in tumour cell growth or viability that may be necessary for inducing a clinical response. Cellular signalling through the oncogenic NOTCH target proteins is critical for cell proliferation and survival, which is obtained through the positive regulation of cell cycle, transcription, translation, and the repression of apoptotic machinery. Inhibition of NOTCH signalling will result in a reduced expression of the target proteins and as a result, a decrease in cellular proliferation and/or an increase of apoptosis is expected, and both of these effects can be quantitated as early response markers. Specifically, it is planned to measure apoptosis markers and Ki67, a cellular proliferation marker, by IHC in pre- and post-treatment tumour biopsy samples and hair follicles, or T-lymphocytes from blood and/or bone marrow samples in T-ALL/T-LBL.

Details on the collection, handling and processing of the required specimens for the biomarkers' analysis will be provided in a separate Laboratory Manual.

### **2.5.6 Clinical Experience**

This is the first clinical study on the safety and efficacy of CB-103 oral capsules for the treatment of patients with locally advanced or metastatic solid tumour and haematological malignancies to date.

As of 20 August 2020, 41 patients (median age 55 years, range 25 to 76 years) with solid tumours have been treated with CB-103 in the dose escalation part of the clinical study at oral doses of 15 mg-600 mg QD. Preliminary safety data indicates that CB-103 is well tolerated with 73.3% of adverse events (AEs) being mild (Grade 1) or 21% moderate (Grade 2) in severity, and 5.7% Grade 3. All AEs were evenly distributed over the dose cohorts with no evidence of dose relation. Cumulatively, a total of 352 AEs has occurred in 41 patients since study initiation, of which 132 AEs (37.2%) in 31 patients were considered related to the study drug. The treatment-related treatment-emergent AEs (TEAEs) most commonly reported ( $\geq 10\%$  of patients) were nausea (24%), diarrhea (20%), dyspepsia (15%), fatigue (12%), and vision blurred (12%).

The majority of treatment-related TEAEs resolved or were resolving at the time of data cut-off without requiring medications or discontinuation of CB-103 dosing. The study includes intense ECG monitoring. There was one related AE of tachycardia Grade 1 (in cohort 2; 30mg QD). Overall, there was no signal of cardiotoxicity and no QTc prolongations have been reported to date.

No events of skin phototoxicity or eye mydriasis have been reported to date in this study. Of the 352 AEs reported, 12 (3.4%) were considered serious adverse events (SAEs) and included abdominal pain, anorexia, atrial flutter, cardiac failure congestive, drug-induced liver injury, duodenal haemorrhage, dyspnoea, general physical condition decreased, respiratory tract infection, spinal cord compression, transaminase increase, and tumour pain. Of these, one SAE was considered related to study drug (drug-induced liver injury), which was reported in a patient with metastatic adenoid cystic carcinoma with extensive liver involvement, treated at an intermediate dose level.

One patient in cohort 8 (600mg) experienced one dose limiting toxicity (DLT). This was an elevation of the gamma-glutamyl transferase (GGT), grade 3, that was asymptomatic and deemed not clinically significant by the investigator. There has been one unrelated SAE with fatal outcome due to respiratory tract infection in cohort 1 (15 mg). No deaths due to drug-related AEs have been reported to date.

CB-103 is rapidly absorbed after oral administration and reaches Cmax within 1 to 2 hours of dosing. Plasma exposure increases with increasing doses. There were no signs of saturated absorption in the dose range tested. The elimination half-life is approximately 20 hours and CB-103 accumulates about 2-fold with repeated daily administration. Steady state concentrations are reached within one week of dosing.

Hair follicles used as surrogate tissue were obtained at pre-defined time points to measure changes in NOTCH target genes expression by CB-103 treatment. In patients in the ongoing phase 1 study, average target gene downregulation on Cycle 2 day 1, 1h post-dose compared to baseline prior to treatment with CB-103 showed a strong dose-dependent down-regulation of several NOTCH target genes, reaching values higher than 70% inhibition at the highest CB-103 dose tested in this series (250mg). Additionally, a sustained time-dependent down-regulation of NOTCH target genes was observed, reaching up to a 90% inhibition after 4 weeks of daily administration of CB-103 at 250mg dose.

Clinically, best response was durable stable disease (SD) with no or only mild AE at doses showing target engagement. Ten patients with ACC had radiologically confirmed SD, of whom 4 patients had a Notch activating mutation or fusion. The Notch status of the other patients is under investigation. Disease control rate (DCR) of 19 ACC patients at 3 months was 68% (DCR defined as number of patients with CR, PR, or SD divided by the number of patients treated).

Based on the safety profile, the Cohort Review Committee declared the dose of 600mg given once daily QD as a safe dose. The MTD was not reached. The Bayesian statistical model allows further dose escalation to 800mg. Because the visual symptoms caused considerable discomfort to some patients, the 600mg dose was declared as provisional RP2D for further exploration in the dose confirmatory cohort. In parallel, a twice daily schedule of CB-103 is being explored.

Emerging clinical data and any safety findings from this study will be summarized in the Investigator Brochure for CB-103.

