### **9.3.5.4 Persistent or Recurrent Adverse Events**

A persistent adverse event is one that extends continuously, without resolution, between patient evaluation time-points. If the initial severity of a persistent adverse event worsens, the entry in the Adverse Event eCRF should be marked as resolved and a new separated entry with the worsening severity should be added. If the event becomes serious, the Adverse Event eCRF should be updated to reflect this.

A recurrent adverse event is one that resolves between patient evaluation time-points and subsequently recurs. Each recurrence of an adverse event should be recorded separately on the Adverse Event eCRF.

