### 5.7.1 Adverse Events

AEs and SAEs will be summarized by cohort by presenting the number and percentage of patients having any event, number of events is also presented; summaries classifying events according to severity (CTCAE) grade, relationship to study drug, outcome and action taken with study drug will be presented. Missing severity, relationship or outcome will be classed as unknown. If a patient experiences the same AE at more than one severity, or with more than one relationship to investigational product, the most severe rating or the stronger causal relationship to investigational product will be given precedence.

All AEs, related AEs, SAEs, related SAEs, AEs with CTCAE Grade  $\geq 3$ , related AEs with CTCAE Grade  $\geq 3$  as well as AEs leading to premature discontinuation, interruption or discontinuation of study drug or to dose modification will be also summarized presenting the number and percentage of patients having an event in each MedDRA system organ class (SOC) and preferred term (PT) category. A patient with more than one occurrence of the same AE in a particular SOC will be counted only once in the total of those experiencing AEs in that SOC.

All AE, and SAE information collected will be listed as appropriate. A separate summary table and a listing including only DLTs will be also provided.

Only treatment emergent AEs, i.e. AEs occurring on or after day of first administration of study treatment, will be included in the event summaries. Non-treatment emergent events (starting prior to exposure to study treatment) will be included in the patient listings and flagged but not included in the summary tables. Where an AE start date is partially or fully missing, and it is unclear as to whether the AE is treatment emergent, it will be assumed that it is.

All deaths overall will be summarized and listed.

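### A worsening adverse event is closed as resolved and re-entered at the higher grade with no link, so the SAP's event-level counts and outcome summary overstate the number of events and their resolution

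*Protocol*

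**What the plan says.** **Recording rule.** Protocol 9.3.5.4 describes a persistent adverse event as one that carries on from one evaluation to the next and does not resolve. If it worsens, "the entry in the Adverse Event eCRF should be marked as resolved and a new separated entry with the worsening severity should be added". No identifier ties the two entries together. The same section has each recurrence of an event that really did resolve entered separately as well. Protocol 9.5.1 uses resolution in its ordinary sense, a return to the baseline grade or better.

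**Analysis rule.** SAP 5.7.1 summarises adverse events by cohort, "presenting the number and percentage of patients having any event, number of events is also presented". It adds that "summaries classifying events according to severity (CTCAE) grade, relationship to study drug, outcome and action taken with study drug will be presented". If a patient has the same event at several severities or relationships, "the most severe rating or the stronger causal relationship to investigational product will be given precedence". A patient with repeats of the same event within a system organ class "will be counted only once in the total of those experiencing AEs in that SOC". There is no rule for which outcome applies to a split event, and none that merges its records for the event count. The general notes in SAP 5.1 define any duration as end date minus onset date plus one.

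**Where event-level figures are used.** Protocol 2.5.6 supports its statement that CB-103 is well tolerated with shares of 352 events in 41 patients: "73.3% of adverse events (AEs) being mild (Grade 1"), 21% Grade 2 and 5.7% Grade 3. It then says, with no count: "The majority of treatment-related TEAEs resolved or were resolving at the time of data cut-off without requiring medications or discontinuation of CB-103 dosing".

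**The concern.** A record closed because the event got worse carries the same outcome as one closed because the patient recovered. In the data set, deterioration and recovery followed by recurrence look alike: a resolved row, then another row.

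Three event-level results are exposed. The number of events rises by one for each worsening. The outcome summary gains one resolved event for each worsening. The grade distribution gains a lower-grade record, which dilutes the share at the highest grade. If an event duration were tabulated, it would be cut short at each change of grade.

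SAP 5.7 calls safety the primary analysis, and Protocol 2.5.6 shows that event-level percentages are used to describe tolerability. A reader of the study report would take the outcome table at face value.

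**Working it through.** **Step 1. Follow one event through both rules.** Take an event that goes from Grade 1 to 2 to 3 and is still ongoing.

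| | Records as entered | Collapsed to one event |
|---|---|---|
| Events | 3 | 1 |
| Resolved | 2 of 3 (67%) | 0 of 1 |
| Grade 3 share of events | 1 of 3 | 1 of 1 |
| Patients with the event | 1 | 1 |
| Patient's worst grade | 3 | 3 |

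The last two rows do not change. The first three do.

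**Step 2. Reproduce the figures in Protocol 2.5.6.** 0.733 × 352 = 258.0, 0.21 × 352 = 73.9 and 0.057 × 352 = 20.1. The whole numbers 258, 74 and 20 sum to 352 and give back 73.3%, 21.0% and 5.7%.

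**Step 3. Bound the effect on grade.** The number of splits is not given, so it is an assumption with a range. Let k2 be the Grade 2 records with a closed predecessor (0 to 74, each predecessor Grade 1). Let k3 be the Grade 3 records with one (0 to 20), of which *a* had a Grade 2 predecessor. After collapsing:

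- Grade 1 = 258 − k2 − (k3 − a)
- Grade 2 = 74 − a
- Grade 3 = 20
- total = 352 − k2 − k3

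| Assumption | G1 / G2 / G3 | Total | G1 % | G2 % | G3 % |
|---|---|---|---|---|---|
| No splits (as stated) | 258 / 74 / 20 | 352 | 73.3 | 21.0 | 5.7 |
| k2 = 7, k3 = 2, a = 0 | 249 / 74 / 20 | 343 | 72.6 | 21.6 | 5.8 |
| k2 = 7, k3 = 2, a = 2 | 251 / 72 / 20 | 343 | 73.2 | 21.0 | 5.8 |
| k2 = 37, k3 = 10, a = 0 | 211 / 74 / 20 | 305 | 69.2 | 24.3 | 6.6 |
| k2 = 37, k3 = 10, a = 10 | 221 / 64 / 20 | 305 | 72.5 | 21.0 | 6.6 |
| k2 = 74, k3 = 20, a = 0 | 164 / 74 / 20 | 258 | 63.6 | 28.7 | 7.8 |
| k2 = 74, k3 = 20, a = 20 | 184 / 54 / 20 | 258 | 71.3 | 20.9 | 7.8 |
| k2 = 0, k3 = 20, a = 0 | 238 / 74 / 20 | 332 | 71.7 | 22.3 | 6.0 |
| k2 = 0, k3 = 20, a = 20 | 258 / 54 / 20 | 332 | 77.7 | 16.3 | 6.0 |

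At most 74 + 20 = 94 of 352 records (27%) could be superseded. The Grade 3 share can only rise, by no more than 2.1 points. This one-way result needs Grade 3 to be the highest grade recorded, as it is in these figures. The Grade 1 share can fall to 63.6% or rise to 77.7%.

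**Step 4. Outcome.** Let R of the 132 related records be resolved or resolving, k of them superseded. The collapsed share is (R − k)/(132 − k), which falls to one half when k = 2R − 132. If R = 67, two superseded records remove the majority; if R = 80, it takes 28; if R = 93, 54. Neither R nor k is given. The share can only fall when superseded records are removed, unless it is already 100%.

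**Step 5. Patient-level rates.** Nausea 24% (10/41), diarrhoea 20% (8/41), dyspepsia 15% (6/41), and fatigue and blurred vision 12% each (5/41) are the same however many records an event has.

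Two inputs need reconciling on their own account. 132/352 is 37.5%, whereas the text gives 37.2% (131/352 or 132/355 would give that). Grades 1 to 3 account for every event, although the same section reports a serious event with fatal outcome.

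**The case against.** The case for leaving the plan alone is substantial. SAP 5.7.1 reports patients first and the number of events second. Its worst-grade and strongest-relationship rule protects severity and relationship for each patient. The confirmatory cohort's primary endpoint (Protocol 4.2.1, SAP 2.5) covers incidence, severity and relationship, and outcome is not part of it. Dose-limiting toxicities are counted per patient. The Cohort Review Committee sees all events of Grade 3 or above and all serious events, and each of these keeps its own record. All adverse event data are listed, so contiguous rows can be traced. SAP 5.7.1 plans no table of event duration. The table shells, which are not available here, may contain further rules. All of this stands and limits the reach of the point. None of it supplies an outcome rule or merges records for event counts in the SAP as written.

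Four stronger readings are tempting and are not supported:

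- *The figures in Protocol 2.5.6 are biased.* The section gives no split count, outcome count or tabulation method. Its data are as of 20 August 2020, before protocol version 4.3 (28 May 2021) and SAP version 2.0 (29 April 2022). They may be affected; that they are is not shown.
- *Worsened events are reported only as milder, resolved ones.* The higher-grade entry is also made and counted, with its own outcome.
- *The error always favours the drug.* Splitting raises the total number of events, which does not, and the Grade 1 share can move either way.
- *The dose decision rested on these percentages.* Protocol 2.5.6 ties the provisional 600 mg choice to the safety profile and to visual symptoms. It does not link it to event shares.

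**Conclusion.** The defect holds at event level. Protocol 9.3.5.4 contradicts its own definition of a persistent event and the meaning of resolution in 9.5.1, and SAP 5.7.1 does not repair it. Followed as written, each worsening adds one extra lower-grade event with a false resolved outcome. The event-level outcome summary then overstates resolution, event counts are inflated, and where Grade 3 is the highest grade its share of events can only be understated.

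The known size is limited. For the Protocol 2.5.6 data, the collapsed Grade 3 share lies between 5.7% and 7.8%. The upper end requires every Grade 2 and Grade 3 record to have had a closed predecessor, which is an extreme assumption. The statement about most related events resolving might be robust or might rest on very few records; the documents do not allow a check. Patient-level incidence and worst-grade tables stand.

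**What to change.** - **Protocol 9.3.5.4 and the eCRF:** replace closure as resolved with an outcome such as *not resolved, grade changed (worsened)*, and link the closed entry to the new one.
- **SAP 5.7.1:** collapse linked records of the same event into one, with first onset, worst grade, strongest relationship and final outcome. For data already entered, use the same preferred term with contiguous dates. Base event counts and outcome summaries on the collapsed event, and any event duration if one is presented.
- **Protocol 2.5.6:** state how the figures were counted, and recompute them only if records were split.

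The cost is one outcome option, a small derivation and a few sentences. No new patient data are needed. Event-level figures may become slightly less favourable.
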